Our long-term goal is to implement cost-effective treatments that reduce the morbidity and mortality associated with alcohol and substance misuse. VA has widely implemented evidence-based cognitive-behavioral therapy (CBT) for treatment of substance abuse disorders (Karlin & Cross, 2014). The primary goal of the current study is to evaluate the clinical effectiveness and cost effectiveness of CM as an adjunct to CBT for AUD. The trial will also explore the potential utility of a long-term abstinence incentive on treatment utilization and alcohol outcomes. We plan to conduct a comparative effectiveness trial with a 2 x 2 factorial design in which 140 veterans with AUD will be proactively recruited and randomized to receive either CM as an adjunct to state-of-the-art evidence-based CBT, or receive CBT alone; and to one of two long-term incentive conditions (i.e., receipt of a monetary incentive for abstinence/low-risk drinking at 6-months vs. no incentive). Specific aims include:

AIM 1: To evaluate the effectiveness of mobile contingency management, as an augment to evidence-based CBT for AUD, on (1) treatment engagement and retention, and (2) reduction in heavy drinking days and abstinence from alcohol at post-treatment, 6-month and 12-month follow-ups.

Hypothesis 1a: Mobile contingency management for AUD will be associated with greater treatment engagement and treatment completion.

Hypothesis 1b: Mobile contingency management for AUD will be associated with decreased self-reported heavy drinking days and increased rates of abstinence from alcohol at each follow-up.

AIM 2: To evaluate the cost effectiveness of CM as an adjunct to evidence-based CBT for SUD in quality adjusted life years (QALY).

Hypothesis 2: CM paired with CBT will result in greater cost-effectiveness compared to the CBT alone as measured by the incremental cost-effectiveness ratio.

AIM 3: To explore the effects of a long-term (six-month) abstinence incentive on (1) treatment utilization and (2) alcohol outcomes at the 6-month and 12-month follow-ups.

Hypothesis 3: A long-term abstinence incentive will (1) increase utilization of AUD aftercare and (2) be associated with reduced heavy drinking days and increased abstinence rates.

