Cost Measurement. Costs to be collected can be grouped into three broad categories: intervention delivery costs, participant time costs, and health care costs. Intervention costs incurred to develop both interventions will be excluded from the analysis as these costs have already been incurred and are thus “sunk” costs. Intervention Delivery Costs for both conditions will be estimated using both standardized estimates and convenience sampling of support staff and our interventionists. The time it takes to prepare for and execute CBT for SUD is specified in the treatment manual but will be assessed through a data tracking system, surveys, and counselor records to validate these estimates. Similar methods will be used to estimate time spent in identifying veterans with AUD, contacting veterans, and training veterans on the use of the mCM smart phone app. To reduce burden, we will not measure every activity for every subject for every occasion. Instead we will collect a convenience sample of observations toward the beginning and the end of the study to account for the fact that there may be a learning curve effect. The size of the convenience sample will depend on the variability we observe in the activity times—the larger the variability the larger the sample we will collect. In addition to labor costs, materials costs, including the cost of the mCM will be included.

Participant Time Costs (i.e., the opportunity costs to participants). This will include the time spent by participants in using the intervention strategies, techniques, or information. As part of the end-of-treatment follow-up, time spent on the intervention materials other than that involved in the treatment sessions will be assessed. In the intervention arm, the number of videos submitted will be used to assess the time involved in providing bioverification as part of mCM. We will derive participant time cost estimates for each group by combining the time estimates with standard wage estimates adjusted for age, gender, and if possible race, derived from the Statistical Abstract of the United States. Because we chose to conduct the cost-effectiveness analysis from the societal perspective, the use of mean wage rates has higher generalizability and validity than self-reported wages by the subjects. *Health care costs* will be obtained from VA medical records for outpatient, inpatient and medication use one year prior to trial enrollment and through the final follow-up.

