Cost and Effectiveness Measurement. Our primary cost effectiveness outcome measure will be the incremental cost-effectiveness ratio (ICER), with costs as the numerator and effectiveness as measured by QALYs as the denominator. Costs will include: intervention delivery costs, participant time costs and health care costs as described above. The QALY is a standardized effectiveness measure, based on the EuroQol (EQ-5D5L), that allows for the comparison of the value of a particular intervention to a broad range of other potential health care investments. Differences in reduction in heavy drinking days and secondary drinking outcomes (e.g., abstinence) among veterans in the mCM+CBT and the CBT comparison group will allow us to identify changes in the QALY effectiveness measure across groups. To estimate the QALYs, we will employ the methods and estimates developed by Barbosa and colleagues (2010), who used a Markov model to assign utility weights to a range of drinking patterns for medical morbidity and mortality, adjusted for health-related quality of life. Incremental costs and effectiveness of mCM+CBT will be compared to those of the CBT comparison group.

D.7. Optional Study Procedure

One of our study therapists, [name], is seeking licensure as a Licensed Professional Counselor, and as part of her supervision, needs to provide video recordings of therapy sessions to her supervisor, [name], MS, LPCS for review. Data will be shared with [name] as view only in a Duke Box folder to which only [name], [name], and [name] have access. Data will be shared in accordance with a data agreement facilitated by Duke’s Office of Research Contracts, and signed by [name] and [name]. This study procedure is fully optional, and is indicated as such during the informed consent process.

D.8. Measures

Participants will complete measures at primary assessment time points (baseline, post-treatment, 6 months post-quit date, and 12 months post-quit date), as well as reporting on alcohol at each CBT session. Follow-ups will be completed in-person.

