Aim 2: To examine the hypothesis that mCM paired with CBT for SUD will be more cost effective over the lifetime than CBT alone, cost-effectiveness analysis (CEA) will be performed using the incremental cost-effectiveness ratio (ICER), with costs as the numerator and effectiveness as measured by quality-adjusted life years (QALY) as the denominator. QALYs incorporate changes in quality of life (morbidity) using a set of values, one for each possible health state, reflecting the relative desirability of the health state (Drummond et al., 2009). Quality of life ratings, or utilities, will be derived from a prior study of the utility of different drinking states that used the standard gamble technique in a community/clinic sample of 200 individuals (Kraemer et al., 2005). The mean utility values (and standard deviations) calculated for each state were as follows: abstinent 0.93 (0.15), moderate drinking 0.88 (0.22), at-risk drinking 0.82 (0.27), meeting criteria for mild AUD 0.75 (0.29), meeting criteria for severe AUD 0.67 (0.29), and in recovery from alcohol dependence 0.83 (0.24). QALY change will be calculated based on change from baseline to 12-month drinking status. Prior to CEA, CBT alone will be assessed for dominance to determine whether it is both less costly and more effective than combined mCM and CBT. In the absence of dominance, an incremental cost-effectiveness ratio (ICER) will be computed to estimate the additional cost required to achieve one additional QALY. Specifically, the ICER combines the costs of the treatments with the QALY changes, using the cost in the mCM group over and above the control, divided by the incremental QALYs in the mCM group over and above the control. Given likely skewed economic data, nonparametric bootstrap resampling will be used to test the sensitivity of the calculated ICERs and cost-acceptability curves estimated to assess the probability that the mCM intervention is cost-effective at thresholds up to \$50,000 or \$100,000 per QALY (Willan & Briggs, 2006). Numerous sensitivity analyses will be conducted to evaluate the robustness of these results given varying estimates of abstinence rates, relapse to any heavy drinking, mortality rates, and long-term costs of sustained alcohol use. Cost-effectiveness analysis will be conducted if the primary outcome is significant; otherwise, a cost minimization analysis will be conducted.

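### Aim 2 has no consistent time horizon: the hypothesis is lifetime, the health care costs stop at the 12-month follow-up, and the QALYs are described both ways

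*Combined protocol and SAP*

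**What the plan says.** **Hypothesis.** Section A, Hypothesis 2, gives no horizon: "CM paired with CBT will result in greater cost-effectiveness compared to the CBT alone as measured by the incremental cost-effectiveness ratio". Section F, Aim 2, adds one: mCM with CBT "will be more cost effective over the lifetime than CBT alone, cost-effectiveness analysis (CEA) will be performed using the incremental cost-effectiveness ratio (ICER").

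**Costs.** D.6 defines the numerator: "Costs will include: intervention delivery costs, participant time costs and health care costs as described above". Health care costs come from VA records for "outpatient, inpatient and medication use one year prior to trial enrollment and through the final follow-up". D.8 puts the assessments at "baseline, post-treatment, 6 months post-quit date, and 12 months post-quit date", so the final follow-up is at month 12 after the quit date. The formula in Section F is narrower still: "the ICER combines the costs of the treatments with the QALY changes".

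**QALYs.** Section F says: "QALY change will be calculated based on change from baseline to 12-month drinking status". D.6 says that QALYs rest on the EQ-5D-5L, and also that they will be estimated with the methods and estimates of a published Markov model. The title of that model in the References refers to lifetime QALYs and health care costs.

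**Beyond month 12.** Section F plans sensitivity analyses on abstinence, relapse, mortality and the long-run costs of continued drinking, but gives no values or method for them. Neither D.6 nor Section F states a horizon length, a discount rate, or a rule for the treatment effect after the last visit. Acceptability is judged at thresholds of $50,000 and $100,000 per QALY.

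**The concern.** An ICER is interpretable only if incremental costs and incremental QALYs accrue over the same period, and a conclusion drawn from it holds only for that period. Here the hypothesis, the numerator and the denominator do not share one stated period. An analyst following the text could produce two quite different ratios, each defensible from some sentence in the plan.

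Cost effectiveness is in the trial's title and in its stated primary goal, and the result is to be read against two fixed thresholds. If the horizon is settled only at the analysis stage, that choice could determine which side of a threshold the result falls on. A lifetime statement would also depend on what happens to the difference between arms after month 12, which the trial does not observe.

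**Working it through.** **Step 1. The two readings.**

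| Element | Reading A | Reading B |
|---|---|---|
| Hypothesis (Section F, Aim 2) | lifetime | lifetime |
| Health care costs (D.6) | to month 12 | to month 12 |
| QALYs | lifetime, by the Markov methods (D.6, References) | change from baseline to month 12 (Section F) |
| Result | numerator and denominator cover different spans | spans match, but the hypothesis goes beyond them |

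Neither reading gives a lifetime ICER with lifetime costs.

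**Step 2. What the mismatch would do under Reading A.** Let C be the incremental cost to month 12, H the discounted incremental cost after month 12, and Q the discounted lifetime incremental QALYs (Q > 0).

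- Mixed ratio: C / Q
- Matched lifetime ratio: (C + H) / Q
- Mixed minus matched: −H / Q

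If less drinking saves later health care costs (H < 0), the mixed ratio is too high and counts against CM. If longer life adds later costs (H > 0), it is too low and favours CM. The documents give no value for H or Q, so neither the size nor the sign of the error can be computed.

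**Step 3. The only CM cost figure in the plan.** The plan states no ICER, incremental cost or QALY gain to reproduce. It does state $611 for reinforcement with perfect adherence (D.4.2, D.9):

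- Tickets: (1 + 2 + 3 + 4 × 7) + 7 × 40 = 34 + 280 = 314
- Cost: 314 × $1.91 + $11 = $610.74, which agrees with $611

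**Step 4. How much horizon alone matters (illustration).** Formula: ICER = cost / (risk difference × utility gain × F), where F = Σ [(1 − w)/1.03]^t for t = 0 to T − 1.

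- From the documents: utility gain 0.93 − 0.75 = 0.18 (mild AUD to abstinent) or 0.93 − 0.67 = 0.26 (severe AUD to abstinent); cost $611, reinforcement only.
- Assumed: 10 percentage points more abstinence with CM; an alternative total cost of $2,000; 3% discount; T = 30 years; yearly loss of effect w of 0, 20% or 50%; a full year of gain in the 12-month case (F = 1). Cost is held fixed throughout.

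Resulting F: 20.19 (no loss), 4.48 (20% loss), 1.94 (50% loss).

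| Utility gain, cost | 12 months | 30 y, 50% loss | 30 y, 20% loss | 30 y, no loss |
|---|---|---|---|---|
| 0.18, $611 | $33,944 | $17,467 | $7,584 | $1,681 |
| 0.18, $2,000 | $111,111 | $57,174 | $24,824 | $5,504 |
| 0.26, $611 | $23,500 | $12,092 | $5,250 | $1,164 |
| 0.26, $2,000 | $76,923 | $39,582 | $17,186 | $3,810 |

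Example: $611 / (0.10 × 0.18) = $33,944, and $33,944 / 20.19 = $1,681. The fall from the 12-month column equals F, so it does not depend on the cost, the risk difference or the utility gain. In the $2,000 rows the longer horizon carries the ratio across a threshold even with half the effect lost each year: from above to below $100,000 in one row, and from above to below $50,000 in the other. In the $611 rows the ratio is below both thresholds at every horizon.

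**The case against.** The strongest reply is that the plan does foresee extrapolation. Lifetime modelling is a legitimate choice. The cited model's title covers health care costs as well as QALYs, and Section F will vary relapse, mortality and long-run costs, so the team may intend to project costs too. This stands in part. The text is ambiguous rather than plainly wrong, and insisting on a 12-month base case over a properly built lifetime model is partly a trade-off. But D.6 brings in the model to estimate QALYs only, its list of costs contains no projected category, and sensitivity analyses without values or method do not define a base case.

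A reader might infer several stronger points that the documents do not support:

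- *That the ratio certainly mixes two spans.* Under Section F's own sentence on QALY change, costs and QALYs both end at month 12. The fault is then only the lifetime hypothesis.
- *That the plan favours CM.* Step 2 shows that the direction depends on later costs, which are unknown.
- *That the error is about 20-fold.* That figure compares a 12-month with a 30-year horizon under undiminished effect. It does not compare a mixed with a matched ratio. CM spending comes early, so a correctly matched lifetime ICER could also be far below the 12-month one.
- *That nothing in the trial shows persistence.* Contingent reinforcement starts at CBT week 3 and lasts eight weeks (D.4.2). The contrasts at 6 and 12 months (Section F, Aim 1) therefore do show persistence up to month 12. The gap is after that.
- *That the plan has chosen not to discount.* It is silent on discounting.

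**Conclusion.** The point holds as an internal inconsistency in the Aim 2 horizon. As written, the plan leads either to about 12 months of costs over lifetime QALYs or to a lifetime conclusion from a 12-month analysis. Because following either description leaves the hypothesis unmatched by the analysis, this is more than missing detail.

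The size of the error cannot be given. The illustration shows only how sensitive an ICER is to horizon: a fall of about 2-fold to 20-fold from 12 months to 30 years, with the upper end requiring 30 years of undiminished effect. It rests on the assumed 3% discount, the assumed rates of loss and costs held fixed. Whether a threshold is crossed also depends on the assumed cost and abstinence difference. The $611 figure presumes perfect adherence and omits staff, equipment, participant time and any difference in health care costs. The sponsor should settle the horizon before the Aim 2 analysis.

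**What to change.** State one window in Section F and D.6, make the ICER's costs and QALYs both cover it, and limit the tested hypothesis and the conclusions at $50,000 and $100,000 to that window. With the data and costs as now specified, this means a 12-month within-trial ICER and removing the reference to lifetime from the tested hypothesis, which also brings it into line with Hypothesis 2 in Section A.

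If a lifetime analysis is kept, present it as a separately labelled model that:

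- projects health care costs as well as QALYs over the same stated horizon;
- discounts both at one stated rate;
- states how the effect is assumed to persist, and includes a scenario in which the difference between arms ends at month 12.

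The cost is SAP wording and one extra model scenario. No new data collection is needed. The price for the sponsor is that the headline ICER may look less favourable than a lifetime figure.

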Our study team will use social media to reach potentially eligible participants. We have developed a Facebook page for posting IRB-approved study flyers and information for this and other studies in the Traumatic Stress and Health Research Laboratory, <https://www.facebook.com/Duke-Traumatic-Stress-and-Health-Research-Lab-379366159145563/>. We plan to place pictures of our study flyers on the Facebook page, and use Facebook's post boost to draw attention to the post. The post itself will say "Enroll now!" or "Now enrolling!" We will also plan to use Facebook ads to target potential participants within a 50-mile radius of Duke. If any participant contacts the email associated with the Facebook page ([contact]), he/she will be sent an automatic email response.

Based on our previous studies, we expect to screen 250 participants to enroll and randomize 140. Eligibility criteria for the current trial include:

- are an enrolled veteran at the DVAHCS for primary care,
- can read/write/speak fluent conversational English,
- have current AUD (meeting past month DSM-5 criteria), and
- are willing to make a quit attempt and/or reduce alcohol use to low risk levels.

Exclusion criteria are:

- have fewer than 3 days of abstinence,
- have a history of clinically significant alcohol withdrawal, as indicated by 1) a score of 10 or more on the Clinical Institute Withdrawal Assessment of Alcohol (CIWA), 2) past medical alcohol detoxification, or 3) a history of seizures or hallucinations during alcohol withdrawal.
- is current imprisoned or hospitalized on an inpatient psychiatric unit,
- have had a seizure as an adult (e.g., child febrile seizures not exclusionary),
- is unwilling to sign a VA consent form to retrieve medical records, or
- is currently receiving professional behavioral treatment for AUD.

Veterans with a history of clinically significant withdrawal will not be eligible to participate, and will be referred to their providers for evaluation of medical management of clinical detoxification.

D.3. Study Screening Session and Randomization

[figure not shown]

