D.8.9. Quality of Life and Health Care Utilization. VA administrative data will be accessed via the VA Corporate Data Warehouse to provide objective measures of VA health care utilization. Our team has extensive experience accessing and utilizing VA data (Elhai, [name], & Ford, 2008; [name], Bosworth, Grambow, Dudley, & [name], 2002; [name], Bosworth, Stechuchak, Strauss, & Butterfield, 2006). Additionally, we will collect self-reported use of non-VA healthcare and 12-step programs and information about insurance coverage. Health care related quality of life will be assessed with the EuroQol (United Kingdom Alcohol Treatment Trial Team, 2005) at baseline and each of the follow-ups.

D.9. Participant Reimbursement

Participants will be paid as follows:

Project Milestone	Amount
Screening visit	\$50
CM abstinence reinforcement	\$611
End-of-treatment visit	\$50
6-month follow-up	\$100
Bioverified abstinence at 6 month follow-up (if randomized to long-term incentive condition)	\$300
12-month follow-up	\$125
TOTAL	\$1236

D.10. Potential Challenges and Solutions

One potential challenge to the success of this project is recruitment and retention. Previous AUD trials in veterans indicate lost-to-follow-up rates near 30% at 12 month follow-up (Hagedorn et al., 2013). We have implemented several methods to increase retention in our trials (e.g., pre-alert letters, birthday cards, reminder

calls, thank you notes) and have obtained excellent retention rates ($>80\%$ at 12-months) in substance using populations (e.g., homeless veterans). We will use these methods and have budgeted to provide an incentive to participants to complete each follow-up. Missing data will be treated as indicative of relapse/heavy drinking. Our pilot data and experience in previous trials indicate that proactive recruitment of veterans with AUD is feasible. To augment our proactive recruitment method, we could include reactive recruitment strategies and include referrals from the SUD clinic at DVHCS. Another potential concern is lost/stolen study equipment. We now have extensive experience with providing veterans with a smartphone and monitoring devices to perform mobile monitoring for CM (e.g., R34AA023877; R01CA196304; 1I01HX001109; 1I01RX001301) and have budgeted for anticipated lost/stolen equipment. Costs of lost equipment will be captured and included in cost analyses.

E. DATA AND SAFETY MONITORING

E.1. Risk/Benefit Ratio

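### Aim 2 takes incremental QALYs as a difference in change from baseline without pre-specifying adjustment for baseline utility, so the ICER denominator may be less precise than the collected data allow

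*Combined protocol and SAP*

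**What the plan says.** Section F, Aim 2 defines the effect measure: "QALY change will be calculated based on change from baseline to 12-month drinking status". The incremental cost is then "divided by the incremental QALYs in the mCM group over and above the control". Aim 2 names no regression, no baseline covariate and no term for the incentive factor. Uncertainty is handled by a nonparametric bootstrap, acceptability curves, and sensitivity analyses on abstinence, relapse, mortality and long-term cost.

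The heavy-drinking-day count models for Aims 1 and 3, in the same section, include both the baseline value of the outcome and the other randomized factor.

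The opening of Section F says that covariate adjustment may be used if unexpected baseline differences appear, and it plans sensitivity analyses on baseline variables. Its list of variables to check includes baseline alcohol consumption but not utility.

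The documents differ on where utilities come from. Section D.6 says: "The QALY is a standardized effectiveness measure, based on the EuroQol (EQ-5D5L"), and it also invokes a published Markov model. Aim 2 says: "Quality of life ratings, or utilities, will be derived from a prior study of the utility of different drinking states". Its hypothesis concerns the lifetime, while its QALY change stops at 12 months. Section D.8.9 collects the EuroQol "at baseline and each of the follow-ups", and drinking status is also recorded at screening, so baseline utility is available under either source.

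**The concern.** A change score uses the baseline by subtracting it, which fixes its slope at 1. If the true regression slope of 12-month utility on baseline utility is below 1, subtraction adds noise and over-corrects any chance difference between arms at baseline. A regression estimates the slope from the data, and in large samples its variance is never larger than that of the change score.

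The QALY difference feeds the ICER, the bootstrap and the acceptability curves at \$50,000 and \$100,000 per QALY. Avoidable variance there makes the cost-effectiveness conclusion less certain. Leaving adjustment to a later decision triggered by observed imbalance also leaves open a post-hoc choice that could affect the result.

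**Working it through.** **The plan's own figures.** The plan gives no power, SD or correlation for QALYs, so there is no stated figure to reproduce on this point. Its power figures concern drinking outcomes, and they do reproduce:
- Effective sample size without attrition: 140 × 3 / (1 + 2 × 0.20) = 300.
- With attrition: 86 × 3/1.4 + 15 × 2/1.2 + 18 = 227.3.
- Detectable d at 90% power (two-sided 0.05 and equal arms assumed): (1.960 + 1.282) × √(2/113.6) = 0.43.

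**Formulas.** Let s0 and s1 be the SDs of utility at baseline and 12 months, and ρ their correlation. The variance of the arm contrast is proportional to:
- change score: s0² + s1² − 2ρ·s0·s1
- baseline-adjusted: s1²(1 − ρ²)

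The two are equal when ρ = s0/s1. With s0 = s1 the ratio, adjusted to change, is (1 + ρ)/2.

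**Route A: EQ-5D utilities (Section D.6).** Equal SDs and ρ are assumptions.

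| ρ | variance ratio | SE ratio | SE reduction |
|---|---|---|---|
| 0.2 | 0.60 | 0.775 | 23% |
| 0.5 | 0.75 | 0.866 | 13% |
| 0.8 | 0.90 | 0.949 | 5% |

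Illustration with an assumed SD of 0.20 and ρ = 0.5, where SE = SD × √(4/N):
- N = 140: change 0.200 × 0.169 = 0.034; adjusted 0.173 × 0.169 = 0.029.
- N = 86 (the plan's 12-month attrition scenario): 0.043 and 0.037.

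These are SEs of a 12-month utility difference. If the change accrues linearly over one year, both halve and their ratio is unchanged.

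**Route B: drinking-state mapping (Aim 2).** Section D.2 requires that entrants "have current AUD (meeting past month DSM-5 criteria"). Baseline utility is therefore taken as 0.75 (mild AUD) or 0.67 (severe AUD). With 30% to 70% severe (assumed), s0 = 0.08 × √(p(1 − p)) = 0.037 to 0.040. Assumed 12-month mixes of the abstinent (0.93), moderate (0.88), at-risk (0.82), mild and severe states give s1 = 0.087 to 0.101. With half severe at baseline:

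| 12-month mix | s1 | ρ | SE ratio |
|---|---|---|---|
| same for mild and severe entrants | 0.091 | 0 | 0.916 |
| moderately dependent on entry state | 0.091 | 0.215 | 0.975 |
| strongly dependent on entry state | 0.097 | 0.425 | 1.000 |

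The reduction is 0% to 8% over the mixes tried, and 2% to 3% at ρ near 0.2. A 12-month SD as low as 0.08 with ρ = 0 would give √(0.0064/0.0080) = 0.894, or 11%.

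In absolute terms, with s0 = 0.04, s1 = 0.09, ρ = 0.2 and N = 140:
- change: √(0.0016 + 0.0081 − 0.00144) × 0.169 = 0.0154
- adjusted: √(0.0081 × 0.96) × 0.169 = 0.0149

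**Chance imbalance under Route B.** With half severe and 70 per arm, the SE of the difference in severe share is √(2 × 0.25/70) = 0.085. A 10-point difference is about 1.2 SE, so one at least that large occurs in roughly a quarter of randomizations. It shifts mean baseline utility by 0.10 × 0.08 = 0.008. The regression slope is ρ·s1/s0 = 0.2 × 0.09/0.04 = 0.45, so the change score over-corrects by 0.55 × 0.008 = 0.0044. This vanishes near ρ = 0.04/0.09 = 0.44.

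**Cost of estimating the slope.** At N = 86, one covariate inflates the SE by about √(1 + 1/82) = 1.006, or 0.6%.

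**The case against.** The strongest objection is that the larger gains belong to a method that Aim 2 does not describe. Aim 2 maps drinking status to published utilities, and on that route the gain is a few percent at most plausible settings. When ρ is close to the SD ratio, the gain is nil and the small cost of estimating the slope could outweigh it. This stands. Section D.6 does name the EQ-5D, so the larger range cannot be dismissed, but the conflict over QALY source comes first. The ranges here also do not cover the Markov or lifetime route.

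Second, the plan does not rule out adjustment. The opening of Section F permits it, and baseline alcohol consumption, which is on the list of variables to check, is closely tied to drinking status. This also stands in part: the accurate statement is that adjustment is not pre-specified. The provision is discretionary, depends on observed imbalance, and names no model for Aim 2.

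A reader might infer three stronger points that the documents do not support:
- **That the ICER is biased.** Under randomization the change-score difference is unbiased, and the bootstrap reflects its variance.
- **That the plan expects a weak utility correlation because the power section uses an ICC of 0.20.** That figure is for smoking abstinence across post-treatment, 3-month and 6-month visits. It is neither a utility nor a baseline-to-follow-up correlation.
- **That the lost precision can be set in dollars against the \$611 of reinforcement.** That sum is an expected total for the reinforcement alone, and the main-phase part assumes perfect adherence. Section D.6 counts staff, participant time and health care costs as well, and cost variance also enters the acceptability curve.

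Finally, the cost-effectiveness analysis runs only if the primary outcome is significant; otherwise Aim 2 falls back to cost minimization.

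**Conclusion.** The point holds as a low-cost improvement in efficiency and pre-specification. Aim 2 fixes the contrast as a difference in change and pre-specifies adjustment for neither baseline utility nor the incentive factor, although the count models for Aims 1 and 3 include both the baseline value and the other factor.

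The benefit of adjusting is modest to moderate on the EQ-5D route (SE about 5% to 23% smaller) and small to nil on the drinking-state route (about 0% to 8%). Both ranges rest on assumed correlations, SDs and state mixes, because the plan gives none for utilities. The drinking-state range further assumes that every entrant is assigned to one of the two AUD utilities. Chance imbalance is a matter of noise in a single trial and does not bias the estimate on average.

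**What to change.** First, reconcile Section D.6 with Section F, Aim 2 by naming one QALY source and one horizon for the primary cost-effectiveness analysis.

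Then pre-specify incremental QALYs as the CM coefficient from a regression of participant QALYs on:
- CM arm
- baseline utility from the same source
- incentive arm
- the comorbid non-tobacco SUD stratum used in randomization (Section D.3)

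Refit the model in every bootstrap resample, with each participant's cost kept paired with their QALYs and the planned multiple imputation applied. State how imputation and resampling are combined. Report the unadjusted difference in change as a sensitivity analysis.

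No new data are needed, since the EuroQol and drinking status are already collected at baseline. The cost is SAP wording plus a small amount of extra code and computing, mainly for imputation within the bootstrap.
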